#### **G. Clinical Trials.gov**

[name] will register the trial on ClinicalTrials.gov as soon as IRB approvals are obtained.

## **BACKGROUND**

Vestibular migraine (VM) was defined by the International Headache Society and Bárány Society as a disorder producing recurrent episodes of vertigo or dizziness accompanied at least 50% of the time by migrainous features in patients with histories of migraine. This randomized controlled trial tested the efficacy of rizatriptan as an abortive treatment for attacks of VM.

## **METHODS**

Patients with VM (N=225) were observed prospectively to confirm the diagnosis. Those who experienced two verified VM attacks within 12 months (N=114) were randomized 2:1 to treat up to three subsequent attacks with rizatriptan 10 mg or placebo orally. The primary outcome was the proportion of attacks with vestibular symptoms (vertigo or unsteadiness/dizziness) reduced from moderate/severe to none/mild at 1 hour after administration of study drug. Secondary outcomes were: (1) proportion of attacks with symptoms resolved at 1 hour, (2) proportion of attacks with symptoms reduced from moderate/severe to none/mild at 24 hours, (3) treatment satisfaction at 48 hours, (4) quality of life at 48 hours, and (5) rates of adverse effects.

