## III. APPROACH

We propose a two-center, randomized, double blind, placebo-controlled, parallel, three-episode, clinical trial of rizatriptan 10 mg oral tablets versus placebo for treating spontaneous vestibular attacks in patients with VM.

Our primary Specific Aim is to test hypotheses 1a-1d that rizatriptan will be:

- 1a. Superior to placebo in reducing the severity and duration of vestibular attacks as measured by:
  - (1) Proportion of treated attacks in which subjects experience a reduction in severity rating from Grade 3/2 to Grade 1/0 at one hour after taking study medication (see below for rating description). This is the main outcome measure; 1a(2)-1d(2) are secondary outcome measures.
  - (2) Proportion of treated attacks in which subjects achieve sustained relief (i.e., vestibular symptom severity rating of Grade 1/0) for 24 hours after taking study medication, without use of non-study therapies.
  - (3) Proportion of treated attacks in which subjects experience freedom from vestibular symptoms (i.e., severity rating of Grade 0) at one hour after taking study medication.
  - (4) Use of fewer non-study therapies after each attack treated with study medication.
- 1b. Superior to placebo in reducing severity of symptoms associated with vestibular attacks as measured by:
  - (1) Proportion of treated attacks in which subjects experience relief (reduction to Grade 1/0) from VM-associated symptoms (e.g., nausea, vomiting, motion sensitivity, gait disturbance, headache, photophobia, and phonophobia) at one hour after taking study medication.
  - (2) Proportion of treated attacks in which subjects achieve sustained relief from VM-associated symptoms for 24 hours after taking study medication without use of non-study therapies.
- 1c. Superior to placebo on treatment satisfaction and health-related quality of life as measured by:
  - (1) Scores on the Treatment Satisfaction Questionnaire for Medication (TSQM) at 48 hours after each attack treated with study medication
  - (2) Scores on the Short Form 12 (SF-12) at 48 hours after each attack treated with study medication
- 1d. Tolerated as well as placebo by patients with VM as measured by:
  - (1) No greater rate of treatment-emergent serious adverse events reported on the NCI Common Toxicity Criteria Scale 4.0^59 obtained 48 hours after each attack treated with study medication.

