**Table 2. Study Procedures and Rating Scales**

Procedures	Visit 1 Enrollment	Observation Phase	Visit 2 Randomization	Treatment Phase	Visit 3 End Point
Obtain informed consent	X				
Abstract medical record data	X				
Verify enrollment criteria	X				
Characterize baseline symptoms	X				
Instruct re Vestibular Symptom Diary	X		X		
Assess & stabilize comorbidity		1 st 3 months			
Review Vestibular Symptom Diary		Monthly	X	Monthly	X
Update health & medication list		Monthly	X	Monthly	X
Randomize for treatment			X		
Instruct re study treatment			X		
Dispense drug/placebo			X		
Treat 3 attacks				X	
Pregnancy Test			X		
Rating Scales					
Dizziness Handicap Inventory 	X		X		X
Anxiety Scale (GAD-7) 	X		X		X
Depression Scale (PHQ-9) 	X		X		X
Vestibular Symptom Diary		X		X	
Common Toxicity Criteria Scale 4.0 				X	
Treatment Satisfaction (TSQM) 				X	
Quality of Life Scale (SF-12) 	X		X	X	X
NEO-PI-3 Personality Inventory 	X				

**E. Outcome and Safety Measures (#1-4 mirror measures used in Phase III registration trials of rizatriptan)**

- 1. Vestibular Symptom Diary.** During Observation and Treatment Phases of the study, subjects will track the frequency of their headaches vestibular symptoms (unsteadiness/dizziness), and sensitivity to potential triggers of attacks (head/body motion, environmental stimuli, specific positions).
- 2. Common Toxicity Criteria Scale 4.0** (National Cancer Institute). A clinician-rated, comprehensive measure of toxicity from study medications in all body systems.
- 3. Treatment Satisfaction Questionnaire for Medication** (TSQM). A validated self-report measure of treatment satisfaction in four domains: effectiveness, side effects, convenience, and global satisfaction. Subjects will be asked whether they think they received rizatriptan or placebo after each dosing
- 4. Short Form 12** (SF-12). A 12-item self-report measure of health-related quality of life in six domains.
- 5. Dizziness Handicap Inventory** (DHI). A 25-item self-report of vertigo, dizziness, functional impairment, and emotional symptoms associated with vestibular symptoms.

6. **Generalized Anxiety Disorder Scale (GAD-7).** A 7-item self-report rating scale for anxiety, a common comorbidity of VM. The GAD-7 has cut-offs for clinically significant levels of anxiety symptoms.

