3. After testing bivariate differences, we will use repeated measures mixed effects models to compare outcome measures between rizatriptan and placebo over time, and examine the effects of covariates on treatment response. As an example, for the special case of binary outcome vertigo severity (Grade 3/2 versus Grade 1/0) and the more general case of ordinal outcome vertigo severity (Grade 3, 2, 1, 0), we will use SAS PROC GLIMMIX to model the logits of cumulative probabilities including vectors for study drug, illness related variables, associated symptoms, rating scales, random effects, and time. The estimates on the linear scale will represent log cumulative odds. The cumulative logits are formed as  $\log \{ \Pr(Y_i \leq j) / \Pr(Y_i > j) \} = X_i \alpha + Z_i \gamma_i + \varepsilon_i$  for  $i=1, \dots, n$ , where  $Y_i$  is the  $n_i \times 1$  vector of the outcome measure for the  $i^{\text{th}}$  patient,  $j=0,1,2,3$ ,  $n_i$  is the number of measurements for the  $i^{\text{th}}$  subject in the period,  $X_i$  is  $n_i \times p$  known predictors (indicator signifying rizatriptan and placebo, and time variable.) The fixed effects parameter vector of  $\alpha$  is  $p \times 1$ .  $Z_i$  is  $n_i \times k$  known predictors, which are associated with the random part of the model, including time-varying and time factors.  $\gamma_i$  is the  $k \times 1$  random effect parameter vector and  $\gamma_i \sim N(0, D)$ ,  $\varepsilon_i$  is  $n_i \times 1$  and  $\varepsilon_i \sim N(0, \sigma^2 I)$ , which is independent of  $\gamma_i$ . Let

$\Sigma_i(\theta) = Z_i D Z_i^T + \sigma^2 I$  with  $\theta$  being the parameter of covariance vector. Integrating out  $\gamma_i$  in the above random effect model, we can write  $Y_i \sim N(X_i \alpha, \Sigma_i(\theta))$ .

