## **RESULTS**

Of 308 treated attacks, 245(79.5%) with moderate/severe vestibular symptoms were used to test study outcomes. On the primary outcome, rizatriptan did not differ from placebo in reducing vertigo [73/153(47.7%) vs. 53/92(57.6%) attacks,  $p<0.28$ ] or unsteadiness/dizziness [29/153 (18.9%) vs. 11/92 (12%) attacks,  $p<0.24$ ]. On secondary outcomes, rizatriptan was superior to placebo in reducing unsteadiness/dizziness [120/149 (80.5%) vs. 52/88 (59.1%) attacks,  $p<0.008$ ] at 24 hours and in treatment satisfaction [regression estimate 11.92, 95% CI (2.33, 21.62),  $p<0.016$ ] and physical well-being [regression estimate 4.55, 95% CI (1.14, 7.97),  $p<0.009$ ] at 48 hours. Rizatriptan caused more mild/moderate fatigue and drowsiness than placebo but otherwise did not differ in side effect burden.

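### Main outcome 1a(1) does not say which vestibular symptom is graded, and the appended summary reports it as two comparisons with no combining rule

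*Combined protocol and SAP*

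**What the plan says.** Section III. APPROACH defines 1a(1) as "Proportion of treated attacks in which subjects experience a reduction in severity rating from Grade 3/2 to Grade 1/0 at one hour" after dosing and adds "This is the main outcome measure; 1a(2)-1d(2) are secondary outcome measures". So there is one primary outcome on one rating.

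The documents describe the rated symptom in different ways:

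- **III.E.1, Vestibular Symptom Diary:** "vestibular symptoms (unsteadiness/dizziness), and sensitivity to potential triggers of attacks".
- **III.J.3, item 3 (model):** "binary outcome vertigo severity (Grade 3/2 versus Grade 1/0").
- **Appended METHODS:** "vestibular symptoms (vertigo or unsteadiness/dizziness) reduced from moderate/severe to none/mild at 1 hour".
- **Appended RESULTS:** the primary outcome appears as two comparisons, vertigo (73/153 vs 53/92) and unsteadiness/dizziness ("29/153 (18.9%) vs. 11/92 (12%) attacks"), each with its own p-value.

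Three parts of III.J depend on 1a(1) as a single outcome. J.1 sets a two-sided type I error of 0.05 and 80% power. J.3 item 4 supports a Phase III trial if 1a(1) is significant in favour of rizatriptan and tolerability is acceptable. J.3 item 7 stops at the interim if the primary outcome differs between arms, or if response is below 25% in both arms.

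**The concern.** A responder rule needs a named rating. Without one, an analyst can grade vertigo, grade unsteadiness/dizziness, take either, take the worse, or require both, and each choice gives a different 1a(1). The summary shows that the gap was filled with two comparisons. The documents do not say whether one significant symptom would have been enough, whether both were needed, or which would prevail if they disagreed.

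Three things are at stake: the 5% error rate behind the go decision, the meaning of the interim efficacy and futility rules, and the meaning of the response proportion itself. On the last, both comparisons use the same denominators, 153 and 92. An attack at Grade 0 or 1 on a symptom before dosing cannot fall from Grade 2–3 on that symptom, so a shared denominator needs explaining.

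**Working it through.** **1. The plan's own figure.** Inputs from III.J.1: 120 subjects at 2:1 (80 vs 40), two-sided 0.05, 80% power, odds ratio 3.2. The control rate used is not stated; I assume 22%, the placebo rate of the earlier triptan trial in vestibular migraine.

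- Treated rate: odds 3.2 × 0.22/0.78 = 0.903, so 0.903/1.903 = 47.4%.
- Pooled rate: (40 × 0.22 + 80 × 0.474)/120 = 0.389. Null SE = √(0.389 × 0.611 × (1/40 + 1/80)) = 0.0944. Alternative SE = √(0.22 × 0.78/40 + 0.474 × 0.526/80) = 0.0861.
- Power = Φ((0.254 − 1.96 × 0.0944)/0.0861) = 79.0%; required N is 123 and the detectable odds ratio is 3.24.

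This reproduces the plan for **one** test. With a 25% control rate, power is 81.2% and N is 117.

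**2. Two tests at 0.05, either one sufficient.** For one look, with independent statistics, two-sided error is 1 − 0.95² = 9.75%, and a false win for rizatriptan is 1 − 0.975² = 4.9%. For correlated statistics (bivariate normal, correlations assumed):

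| Correlation | Any false significance (nominal 5%) | False win for rizatriptan (nominal 2.5%) |
|---|---|---|
| 0 | 9.75% | 4.9% |
| 0.5 | 9.1% | 4.5% |
| 0.8 | 7.8% | 3.9% |

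The right-hand column bears on the go rule, which needs a result favouring rizatriptan. The middle column bears on the interim rule, which stops for a difference in either direction.

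**3. Both required.** Error does not inflate. If both symptoms have the planned effect (22% control, odds ratio 3.2), power runs from 0.79² = 62% (independent) to 79% (perfectly correlated).

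**4. Either sufficient, error controlled.** With Bonferroni at 0.025 each, power per symptom at N = 120 falls from 79.0% to 69.0%, N rises from 123 to 150, and the detectable odds ratio rises from 3.24 to 3.63. Hochberg rejects whenever Bonferroni does, so it loses no more than this.

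**5. The reported comparisons (RESULTS).**

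- Vertigo: 73/153 − 53/92 = 47.7% − 57.6% = −9.9 points. Crude odds ratio (73 × 39)/(80 × 53) = 0.67, 95% CI 0.40 to 1.13.
- Unsteadiness/dizziness: 29/153 − 11/92 = 19.0% − 12.0% = +7.0 points. Crude odds ratio (29 × 81)/(124 × 11) = 1.72, 95% CI 0.81 to 3.64.

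These intervals ignore repeated attacks per subject. Crude chi-square p-values are 0.13 and 0.15; the reported bounds of 0.28 and 0.24 are larger, as one would expect if repeated attacks were modelled.

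**6. The futility rule.** At these final rates vertigo is above 25% in both arms (47.7%, 57.6%), so the trial continues. Unsteadiness/dizziness is below 25% in both (19.0%, 12.0%), so it stops. The interim rates are not given, so this is an illustration only. It needs no multiplicity argument.

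**7. The composite.** It cannot be recovered from the margins. Taking the denominators at face value, either symptom reduced lies between 73/153 = 47.7% and (73 + 29)/153 = 66.7% on rizatriptan, and between 53/92 = 57.6% and (53 + 11)/92 = 69.6% on placebo. Both reduced lies between 0 and 19.0%, and between 0 and 12.0%.

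**8. Power at the reported placebo rates** (odds ratio 3.2, N = 120, one test at 0.05, subject as unit as in the plan): 78% at a placebo rate of 57.6%, but 61% at 12.0%, where the detectable odds ratio is 3.98.

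**The case against.** The strongest reply is that the plan has one main outcome and that only an appended results summary splits it. That is correct. A reader might infer that the trial planned two primary tests at 0.05 each; the documents do not support this. The 0.05 belongs to the single planned outcome, and the summary states no level or success rule for either comparison.

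The symptom wording can also be read more kindly. The diary sentence is garbled and speaks of frequency ("track the frequency of their headaches vestibular symptoms (unsteadiness/dizziness"). Section IV.D.3 says that vertigo, headache and associated symptoms are each rated 0–3. The model in J.3 is offered as an example. Measure 1a(2) and the treatment trigger in III.D.4 refer to vestibular symptoms in general, which would fit one overall rating. 1a(1) points to a rating description further on, and none is in the text available, so one may exist. This weakens any claim of outright contradiction. It does not supply a definition, and a single overall rating is hard to square with two reported primary comparisons.

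Three further readings go too far. The first is that the trial's conclusion rests on a false positive: both tests were null, and adjustment would not change that. The second is that the drug acts in opposite directions on the two symptoms: these are point estimates, and both crude intervals include 1. The third is that ineligible attacks were counted: RESULTS says only that 245 attacks with moderate/severe vestibular symptoms were used, not how an attack at Grade 0/1 on one symptom was scored.

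**Conclusion.** The point holds as a gap in the endpoint definition with practical consequences. 1a(1) does not identify the rating it uses, and the appended summary shows the outcome being reported in two ways without a rule to combine them.

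The size depends on the rule that is missing. If either symptom suffices, error on 1a(1) roughly doubles at worst: 9.75% two-sided, or 4.9% for a false win for rizatriptan. This assumes 0.05 per test, which is inferred, and independence; positive correlation lowers both figures. If both are required there is no inflation, but power is about 62–79% under the planned effect. The futility rule's dependence on the choice of symptom stands without either assumption, though it is shown at final rather than interim rates.

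The shared denominators are an open question, not a demonstrated error. The reported null result on the primary outcome is not called into doubt by multiplicity.

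**What to change.** Define 1a(1) once, in identical words in III. APPROACH and III.J, covering the symptom or combination, pre-dose eligibility and the responder rule. One workable example: for each treated attack take the worse of the vertigo and unsteadiness/dizziness grades, require it to be 2–3 pre-dose, and count a response if it is 0–1 at 1 hour. Make one test at 0.05. If both symptoms are to stay primary, use Hochberg and say so in the go rule. State that the interim efficacy and futility rules use the same definition.

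Report each symptom as secondary, using only attacks at Grade 2–3 on that symptom pre-dose. State how many of the 153 and 92 attacks were at Grade 0/1 on each symptom and how they were scored.

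The cost is wording and analysis if both grades were recorded for each attack, as the two reported comparisons suggest. The real downside is that a worse-of composite may have a lower response rate, which the reported figures cannot supply. The detectable odds ratio of 3.2 should therefore be rechecked at the composite's expected placebo rate. Because results are already reported, any rule applied to this dataset must be labelled post hoc.

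### The appended summary's five secondary outcomes do not match the nine pre-specified in Section III, and the 24-hour outcome has lost its sustained-relief and no-rescue conditions without explanation

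*Combined protocol and SAP*

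**What the plan says.** **Protocol.** Section III (Approach) names 1a(1) as primary and continues: "This is the main outcome measure; 1a(2)-1d(2) are secondary outcome measures". Four of those measures matter most here:

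- 1a(2): vestibular symptoms at Grade 1/0 "for 24 hours after taking study medication, without use of non-study therapies".
- 1a(4): "Use of fewer non-study therapies after each attack treated with study medication".
- 1b(1): the proportion of attacks in which "subjects experience relief (reduction to Grade 1/0) from VM-associated symptoms" at 1 hour.
- 1b(2): the proportion in which "subjects achieve sustained relief from VM-associated symptoms for 24 hours after taking study medication without use of non-study therapies".

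Section III.J.3, item 4, applies the three-step analysis to every outcome measure under hypotheses 1a to 1d. The same item refers to the secondary measures as 1a(2) to 1c(2) and makes 1d(1) and 1d(2) part of the principal result. Sections III.D.4 and III.G let subjects take other medication for residual symptoms from 1 hour after the study capsule. Section III.D.4 has these treatments reported to study personnel.

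**Appended summary.** METHODS states: "Secondary outcomes were: (1) proportion of attacks with symptoms resolved at 1 hour". The other four items are symptoms at most mild at 24 hours, treatment satisfaction at 48 hours, quality of life at 48 hours, and how often adverse effects occurred. RESULTS gives the primary comparison, three quantified secondary results and one sentence on side effects.

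**The concern.** The METHODS list is numbered and closed, so it reads as a statement of what the secondary outcomes were. It is shorter than the protocol's list, and two of the items it keeps are worded differently. No section gives a reason or a date.

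Three things are at stake.

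1. **Rescue.** Once other medication is permitted from 1 hour, a 24-hour rating reflects study drug plus whatever else was taken. The protocol dealt with this twice, through the no-rescue condition in 1a(2) and through 1a(4). Neither appears in the summary, so its 24-hour and 48-hour results cannot be read against rescue use by arm.
2. **Hypothesis 1b.** The summary reports nothing on associated symptoms. Headache is one of them, and Section I.E cites a three-patient case series in which triptans resolved vertigo but induced or aggravated headache.
3. **Tolerability.** Section III.J.3 ties the Phase III decision partly to 1d(1) and 1d(2). CONCLUSIONS describes the drug as well tolerated, but the summary gives neither a serious-event rate nor a discontinuation rate.

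**Working it through.** The check sets the two lists side by side, counts, and then looks in RESULTS for a figure for each item.

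| Protocol, Section III | Summary, METHODS | Summary, RESULTS |
|---|---|---|
| 1a(2) sustained 24-hour relief, no non-study therapy | Item 2, altered: at most mild at 24 hours; sustained and no-rescue conditions gone | Unsteadiness/dizziness 120/149 vs 52/88; vertigo not given |
| 1a(3) Grade 0 at 1 hour | Item 1 | No figure |
| 1a(4) non-study therapies | Absent | None |
| 1b(1) associated symptoms, 1 hour | Absent | None |
| 1b(2) associated symptoms, sustained 24 hours | Absent | None |
| 1c(1) TSQM, 48 hours | Item 3 | 11.92 (95% CI 2.33 to 21.62) |
| 1c(2) SF-12, 48 hours | Item 4 | Physical well-being 4.55 (1.14 to 7.97) |
| 1d(1) serious adverse events | Item 5, widened to adverse effects in general | Words only |
| 1d(2) discontinuation for adverse events | Absent, unless read into item 5 | None |

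**Count of absent measures.**

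- Nine measures, altered ones counted as kept: 9 − 5 = 4 (1a(4), 1b(1), 1b(2), 1d(2)); 4/9 = 44%.
- The same, with discontinuation read into item 5: 4 − 1 = 3; 3/9 = 33%.
- Altered 1a(2) and 1d(1) counted as not kept: 4 + 2 = 6; 6/9 = 67%.
- Seven measures (1a(2) to 1c(2), as Section III.J.3 puts it): 7 − 4 = 3; 3/7 = 43%.

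The range is three to six. 1a(4), 1b(1) and 1b(2) are absent in every version.

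**Printed figures.** 120/149 = 80.5% and 52/88 = 59.1%, as printed, a difference of 21.4 percentage points. The 1-hour vertigo figures also reproduce: 73/153 = 47.7% and 53/92 = 57.6%. Vertigo was therefore 57.6 − 47.7 = 9.9 points lower on rizatriptan at 1 hour, and its 24-hour counterpart is the figure not shown.

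**What the altered 24-hour definition could hide.** The documents give no rescue use by arm, so this step is an illustration under an assumption. Under 1a(2) as pre-specified, some attacks now counted as responses would be reclassified. If all reclassified attacks were on rizatriptan, the arms would be level when its responses fell to 149 × 52/88 = 88, that is, after 120 − 88 = 32 of 120 responses (27%). If all were on placebo, the gap would widen beyond 21.4 points. The direction of any change cannot be determined from what is reported.

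**The case against.** The strongest reply is that the summary is an abstract. It consists of four short blocks after the reference list, nothing says that it replaces Section III, and the protocol still carries all nine measures with a commitment to analyse them. This stands, and it limits the point. A reader might infer that outcomes were removed from the plan, or that hypothesis 1b was never tested. The documents do not support either: absence from a short summary does not show absence from the analysis, and a fuller report may exist that is not part of this document. What brevity does not explain is a closed list of what the secondary outcomes were, or a changed definition of one of them.

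A reader might also infer deliberate selection, because the three secondary results with numbers all favour rizatriptan. The summary does not bear that out. It reports the null primary result first with full counts, including the numerically lower vertigo response on rizatriptan. It says that rizatriptan caused more fatigue and drowsiness, though without figures, and it concludes that benefits were limited.

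On associated symptoms, Section III.D.4 does have them rated at dosing and after it, so measurement is not in question, only reporting.

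Finally, secondary measures were not powered (Section III.J.1), and the principal result rests on 1a(1) plus tolerability. That is correct and limits the consequence for efficacy. It does not cover 1d(1) and 1d(2), which are part of that principal result.

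**Conclusion.** The point holds as an unexplained mismatch between the secondary outcomes in the summary and those in Section III, with incomplete reporting inside this document. Three to six pre-specified measures are not on the summary's list. The range arises because Section III gives nine secondary measures and Section III.J.3 implies seven, and because two measures are altered and one may be folded into another.

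The most consequential item is the change to 1a(2). The 80.5% versus 59.1% result is the only positive symptom result, and it is reported without the conditions that the protocol attached to 24-hour relief. It would be wrong to conclude that rescue medication explains the difference: rescue use by arm is not given, and its effect could go either way.

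The null primary result is untouched. The conclusion assumes only that the definition in Section III stands and that the document contains no explanation elsewhere.

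**What to change.** 1. Align the METHODS list in the summary with Section III, and settle whether 1d(1) and 1d(2) are secondary measures or part of the principal result, since Sections III and III.J.3 differ.
2. Report 1a(2) as pre-specified (sustained, no non-study therapy) beside the 24-hour result now shown.
3. Report by arm, with estimate and 95% CI whether or not significant: 1a(3), vertigo at 24 hours, 1a(4), 1b(1) and 1b(2), 1d(1) and 1d(2).
4. Label any outcome that was changed as changed, with the date and reason.

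This needs no new data collection if Sections III and III.D.4 were followed. The sources are the symptom diary, the additional-treatment reports and the adverse-event records, including discontinuations. The cost is tabulation and a few lines of text.
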